6. GENERAL ANALYSIS DEFINITIONS

6.1 TREATMENT(S)

For basic study information on treatments, please refer to NIS Protocol Section 4. The technical specification for treatment set-up is described in the analysis data set (ADS) plan.

For efficacy analyses, data up to 7 days after last treatment intake will be considered as on treatment for HbA1c

For safety analyses, data up to 7 days after last treatment intake will be considered as on treatment for AE.

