6. INVESTIGATIONAL PLAN

6.1 VISIT SCHEDULE

The investigators will enrol patients who are prescribed Trazenta[®] Tablets. The observation time points will be as follows: before administration of Trazenta[®] Tablets (baseline), at 12 weeks, 26 weeks, 40 weeks, 52 weeks, 64 weeks, 78 weeks, 104 weeks, 130 weeks and 156 weeks after the start of administration, and at the time of discontinuation of administration.

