5.4 OTHER VARIABLE(S)

Demographic and baseline characteristics

- Sex (Male, Female)
- Age [years]
 - Actual age based on first administration of Trazenta®
- Age categories 1: \leq 50 years, 51 to 64 years, 65 to 74 years, \geq 75 years
- Age categories 2: <65 years, >65 years
- Height [cm]
- Body weight [kg]
- Body weight categories: \leq 50 kg, >50 to 70 kg, >70 to 90 kg, >90 kg
- Body mass index (BMI) [kg/m²]
 BMI [kg/m²] = weight [kg] / (height [m])²
- BMI categories 1: $<25 \text{ kg/m}^2$, 25 to $<30 \text{ kg/m}^2$, $\ge 30 \text{ kg/m}^2$
- BMI categories 2: $<25 \text{ kg/m}^2$, $\ge 25 \text{ kg/m}^2$
- BMI categories 3: $<30 \text{ kg/m}^2$, $\ge 30 \text{ kg/m}^2$
- Waist circumference [cm]
- Renal dysfunction: estimated glomerular filtration rate (eGFR) [mL/min/1.73m²]
- eGFR categories 1: ≥90 mL/min/1.73m²(Normal), 60 to <90 mL/min/1.73m²(Mild), 30 to <60 mL/min/1.73m²(Moderate), 15 to <30 mL/min/1.73m²(Severe), <15 mL/min/1.73m² (Endstage)

- eGFR categories 2: >60 mL/min/1.73m², <60 mL/min/1.73m²
- Hepatic dysfunction categories 1: (>ULN [35 U/L] of AST, >ULN of ALT [35 U/L], >ULN of total bilirubin [17 umol/L], or >ULN of ALP [120 U/L]), or other

In case > ULN of AST and CK increase (>400 U/L), patients do not include in hepatic dysfunction.

Conversion factors:

For total bilirubin: $17.102787754404 \times [mg/dL] = [umol/L]$ For AST, ALT, ALP: [IU/L] = [U/L]

Hepatic dysfunction categories 2: $\leq 1*ULN$, $\geq 1*ULN$ to $\leq 2*ULN$, $\geq 2*ULN$ to \leq 3*ULN, >3*ULN

Note: worst value of AST, ALT, total bilirubin, or ALP will be used for the categorization

- Hepatic dysfunction categories 3: (Yes, No, Unknown)
 - Hepatic disorders (Narrow) (SMQ 20000005)
 - Biliary disorders (Narrow) (SMQ 20000118) Note: Presence at baseline is yes
- Patient status: (In patient, Out patient)
- Indication (Type II diabetes mellitus, Other)
- Smoking status (Never, Ex-smoker, Smoker, Unknown)
- Duration of diabetes (≤1 years, >1 to 5 years, >5 years, Unknown) [First administration of Trazenta® (or other oral antidiabetic drug) – first diagnosis of type 2 diabetes mellitus + 1 (if negative value due to the missing and imputation, then 1)] / 365.25
- Hypersensitivity factor (Yes, No, Unknown)
- Concomitant diagnosis (Yes, No, Unknown)
- Cardiovascular (SMQ) history (Yes, No, Unknown)
 - Ischemic heart disease (SMO: 20000043)
 - Cardiac failure (SMQ: 20000004)
 - Cerebrovascular disorders (SMQ: 20000060)

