6.3 SUBJECT SETS ANALYSED

The following two analysis sets are defined as in NIS Protocol Section 7.3. The safety set will be the basis of all demographic, baseline and safety analyses. Efficacy analysis will be on basis of the efficacy set.

• Safety set:

This patient set includes all patients who had no invalid registration, who were dispensed Trazenta[®] and were documented to have taken at least one dose of Trazenta[®].

• Efficacy set:

This patient set includes all patients with Trazenta[®] in the safety set who have a baseline and at least one available on-treatment HbA1c value.

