6.6 HANDLING OF MISSING DATA AND OUTLIERS

Missing or incomplete AE dates are imputed according to BI standards (see "Handling of Missing and Incomplete AE Dates"). (2)

No imputation will be performed in efficacy and safety analyses.

Missing or partial date information will be replaced according to following rules.

YEAR	MONTH	DAY	YMD	DT
"Unknow	n" (tick-box)	UNKNOWN		
<2007	Null	Null	2007	2007/07/01
уууу	Null or "Unknown"	Null	уууу	yyyy/07/01
уууу	Mm	Null or "Unknown"	yyyymm	yyyy/mm/15
уууу	Mm	"First ten days of the month"	yyyymm "First ten days of the month"	yyyy/mm/01
уууу	Mm	"Second ten days of the month"	yyyymm "Second ten days of the month"	yyyy/mm/11
уууу	Mm	"Third ten days of the month"	yyyymm "Third ten days of the month"	yyyy/mm/21

If the date of data which is collected as after treatment of Trazenta[®] in the CRF is before start of Trazenta[®], these data are regarded as erroneous and will be set to missing.

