7.8 SAFETY ANALYSIS

7.8.1 Adverse events

Unless otherwise specified, the analyses of adverse events (AEs) will be descriptive in nature. All analyses of AEs will be based on the number of patients with AEs and NOT on the number of AEs.

Furthermore, for analysis of AE attributes such as duration, severity, etc. multiple AE occurrence data on the case report form, will be collapsed into AE episodes provided that all of the following applies:

- The same MedDRA lowest level term was reported for the occurrences
- The occurrences were time-overlapping or time-adjacent (time-adjacency of 2 occurrences is given if the second occurrence started on the same day or on the day after the end of the first occurrence)
- Treatment did not change between the onset of the occurrences OR treatment changed between the onset of the occurrences, but no deterioration was observed for the later occurrence

For further details on summarization of AE data, please refer to the guideline 'Handling and summarization of adverse event data for clinical trial reports and integrated summaries' (1).

AE analyses will be carried out after integrating AE data from CRF and AE data from perceive system.

In addition, AEs coded as "no adverse event" will not be included in the AE analyses.

Two overall summaries of AEs will be presented. One will be also made for patients including those who were not treated add-on therapy at baseline (i.e. all patients with Trazenta® treatment). Another one will include patients only with add-on therapy at baseline (i.e. safety set). The frequency of patients with AEs,ADRs, and serious AEs will be also summarised by primary SOC and PT in each patient set.

The frequency of patients with ADRs and with serious AEs will be summarised by treatment (background medication and total), primary SOC and PT. AEs will also be reported by intensity.

To compare risks of overall ADR in different patient subgroups, frequency tabulation stratified by different patient subgroups will be provided with odds ratios and exact 95% confidence intervals whenever specified (see Section 6.4). Logistic regression will be used for odds ratio.

In addition, summaries for the time to onset of first episode for the ADRs will be tabulated, by duration (>0 to 12 weeks, >12 to 26 weeks, >26 to 40 weeks, >40 to 52 weeks, >52 to 64 weeks, >64 to 78 weeks, >78 to 104 weeks, >104 to 130 weeks, >130 to 156 weeks, >156 weeks, unknown), primary SOC, and PT.

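### Can a partial stop date close the 7-day adverse-event window before the true last dose and distort the safety results?

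*SAP*

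**What the plan says.** SAP 6.1 sets the on-treatment limit for adverse events: "For safety analyses, data up to 7 days after last treatment intake will be considered as on treatment for AE". HbA1c has the same 7-day limit. The section leaves the technical treatment set-up to the analysis data set plan.

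SAP 6.6 deals with dates in two parts. For adverse events, "Missing or incomplete AE dates are imputed according to BI standards". It then rules out imputation in the efficacy and safety analyses, and next says "Missing or partial date information will be replaced according to following rules". In the table, a year alone becomes 1 July and a year with month becomes day 15. The three ten-day periods become day 1, 11 and 21; the last of these is the row "Third ten days of the month". No row or sentence names the Trazenta stop date.

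The label has one visible selecting role. Under SAP 6.3 the efficacy set takes patients who "have a baseline and at least one available on-treatment HbA1c value", and Protocol 6.1 plans an observation "and at the time of discontinuation of administration". In SAP 7.8.1, ADRs and serious events "will be summarised by treatment (background medication and total), primary SOC and PT". That section does not mention the on-treatment label and refers to a sponsor guideline for further detail.

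**The concern.** Read plainly, the general date table covers any partial date not sent elsewhere, and only adverse-event dates are sent elsewhere. The ten-day rows always take the first day of the period, whereas the month-only and year-only rows take the middle. For a stop date the ten-day error therefore runs one way, towards stopping too early, and it can exceed the 7-day allowance. An event on a day when the patient took the drug could then be labelled off treatment. An HbA1c value taken at discontinuation could lose its on-treatment status in the same way. SAP 5.4 protects diabetes duration against an imputation artefact ("if negative value due to the missing and imputation, then 1"), while SAP 6.1 has no comparable safeguard.

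A second point concerns display. Protocol 5.2.2.1 makes every new cancer a serious event whatever the interval since stopping, so some events will begin after day 7. SAP 7.8.1 does not say whether they enter the main tables or are shown apart. ADR incidence is the primary safety endpoint, so two programmers might count differently.

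**Working it through.** The 7 days are a rule, not a derived figure, so there is nothing to reproduce. The check is how far the SAP 6.6 table could move a stop date if it were applied to one.

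**Inputs.** Window of 7 days (SAP 6.1); imputed days 1, 11, 21, 15 and 1 July (SAP 6.6); planned day 1,092 for week 156 (SAP Table 6.7: 1). Assumption: the true last-intake day is uniform over the unknown period.

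**Formulas.** Early shift s = true day − imputed day. The last-intake day is outside the window when s > 7. Intake days mislabelled = max(0, s − 7).

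**Ten-day rows**

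| Period | s | Outside | Intake days mislabelled, mean |
|---|---|---|---|
| Days 1–10, set to 1 | 0 to 9 | 2/10 | (1+2)/10 = 0.30 |
| Days 11–20, set to 11 | 0 to 9 | 2/10 | 0.30 |
| Days 21–31, set to 21 | 0 to 10 | 3/11 | (1+2+3)/11 = 0.55 |
| Days 21–30, set to 21 | 0 to 9 | 2/10 | 0.30 |
| Days 21–28, set to 21 | 0 to 7 | 0/8 | 0 |

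Over a 365-day year:

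- Stop days outside: 12×2 + 12×2 + 7×3 + 4×2 + 0 = 77; 77/365 = 21.1%.
- Intake days mislabelled: 12×3 + 12×3 + 7×6 + 4×3 + 0 = 126; 126/365 = 0.35 day per affected patient. Against 1,092 days, 0.35/1,092 = 0.03%.
- Mean shift: (12×45 + 12×45 + 7×55 + 4×45 + 28)/365 = 1,673/365 = 4.6 days, so the window left after the true last intake averages 2.4 days instead of 7.

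**Coarser rows**

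- Month only, set to day 15: outside for 7×9 + 4×8 + 6 = 101 of 365 stop days (27.7%). Intake days mislabelled: (7×45 + 4×36 + 21)/365 = 480/365 = 1.3.
- Year only, set to 1 July: outside for 176 of 365 (48%), so the label says little. This row is already mid-period.

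**Does the table govern the stop date?** Four indications, none conclusive:

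- SAP 6.1 puts treatment set-up in another document.
- The no-imputation sentence stands directly before the table. It may concern values only, but it does not support using imputed dates to label events.
- One row maps years before 2007 to 1 July 2007. That fits historical dates such as first diagnosis and cannot be a stop date in a study whose protocol carries a 2013 date.
- The exposure categories in SAP 7.7, built on the treatment end date, have no unknown class. The onset categories in SAP 7.8.1 do.

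**Would the label change a result?** An ADR is defined by causality (Protocol 7.3.3, SAP 7.8.1), not by time since last intake. The tables in SAP 7.8.1 are split by patient set, background medication, organ class and term, intensity, subgroup and onset time, and none visibly by on- or off-treatment status.

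For HbA1c, a reading past the shifted cut-off is replaced by the patient's previous on-treatment value. The patient leaves the efficacy set only if there is none. Let f be the share of the set with a ten-day partial stop date and a reading on the last-intake day, and d the mean difference between that reading and the one before. The mean change then moves by about 0.21 × f × d. Readings some days after stopping are lost more often, but the shift cannot exceed f × d with f counting those patients too.

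**The case for a change.** The strongest case for a change is that nothing exempts the stop date, the ten-day rows err in one direction only, and the remedy is cheap. Setting the ten-day rows to day 5, 15 or 25 would hold the early shift to 5 or 6 days and bring the 77 of 365 down to 0. The stop date also feeds exposure and the collapsing of events into episodes. Serious events must be reported whether or not the drug has been given, so later-onset events will occur even though Protocol 6.2.3 plans no follow-up.

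The arithmetic and the literal reading both stand, and the SAP could have been more explicit. But 21% is a share of possible stop days, not of events or treatment time; the corresponding loss is 0.35 intake day per affected patient. Events may cluster around stopping, which would raise the effect, though the documents give no figure for this. The mid-period rule would count up to 4 off-drug days as on treatment and would leave the rows with the larger errors as they are. An undetermined label for those rows would still need a rule for tabulating it. The SAP 5.4 provision only resets a negative duration, so it is no precedent for guarding a window. A note in SAP 4 adds nothing: SAP 3 describes the SAP as technical elaboration, and the protocol synopsis already ties HbA1c to treatment.

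**Conclusion.** This is a gap that analysts fill sensibly, and no change to the plan is needed. If the SAP 6.6 table were applied to stop dates, the 7-day window could close before the last dose for 21% of possible stop days under the ten-day rows. The mean loss would be 0.35 intake day per affected patient (1.3 days in the month-only row). These figures assume a uniform true date. The number of such patients cannot be derived and is probably small.

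The step from imputed date to altered result is not shown. The table is not stated to govern the stop date, ADRs are defined by causality, and no visible adverse-event table filters on the label. The analysis of HbA1c is affected only through values near discontinuation. The ADR incidence and the mean HbA1c change are both descriptive and would stay sound.

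This rests on the visible text. The analysis data set plan and the adverse-event guideline were not available. They are the natural places for the stop-date rule and the display of later-onset events.

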3. DESCRIPTION OF DESIGN AND STUDY POPULATION

3.1 OVERALL DESIGN AND PLAN

This PMS is a prospective study using a continuous investigation system. Patients with type 2 diabetes mellitus who are treated as add-on therapy are included in the surveillance. No specific criteria (e.g., demographics, baseline characteristics, concomitant drugs in use) are defined for patient enrolment.

Planned number of patients to be entered and have at least one observation after treatment is 3,000. Patients with type 2 diabetes mellitus who are treated with anti-diabetic drugs and have never received Trazenta® Tablets will be enrolled in the surveillance. It is exclusively at the physician's discretion whether to initiate linagliptin on patients.

Patients administered Trazenta[®] Tablets will be registered preferably within 14 days from the day of first administration. Each patient will be observed for 156 weeks (approximately 36 months) after start of the treatment with this product until the end of the PMS or at premature discontinuation and dropout from the PMS. Observations are made at the following time points: before first administration of Trazenta[®] (baseline) and 12, 26, 40, 52, 64, 78, 104, 130 and 156 weeks after the start of treatment, or at discontinuation.

There are 3 eCRFs for 0-26 (Book 1), 40-78 (Book 2) and 104-156 weeks (Book 3) individually.

At 26, 78 and 156 weeks after the start of treatment or at discontinuation, data are to be transmitted immediately after entered into eCRF. In case of occurrence of any adverse events, data in corresponding observation period should be immediately entered into eCRF and transmitted.

Proprietary confidential information © 2013 Boehringer Ingelheim International GmbH or one or more of its affiliated companies

[figure not shown]

Figure 3.1: 1 Overall design of PMS

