5.2.2 Assessment of adverse events

5.2.2.1 Definitions of adverse events

Adverse event

An AE is defined as any untoward medical occurrence, including an exacerbation of a preexisting condition, in a patient in a PMS who received a pharmaceutical product. The event does not necessarily have to have a causal relationship with this treatment.

Serious adverse event

A SAE is defined as any AE which results in death, is immediately life-threatening, results in persistent or significant disability / incapacity, requires or prolongs patient hospitalisation, is a congenital anomaly / birth defect, or is to be deemed serious for any other reason if it is an important medical event when based upon appropriate medical judgment which may jeopardise the patient and may require medical or surgical intervention to prevent one of the other outcomes listed in the above definitions.

An AE which possibly leads to disability will be reported as an SAE. Every new occurrence of cancer will be reported as a SAE regardless of the duration between discontinuation of the drug and the occurrence of the cancer.

Intensity of adverse event

The intensity of the AE should be judged based on the following:

Mild: Awareness of sign(s) or symptom(s) which is/are easily tolerated Moderate: Enough discomfort to cause interference with usual activity

Severe: Incapacitating or causing inability to work or to perform usual

activities

Proprietary confidential information © 2013 Boehringer Ingelheim International GmbH or one or more of its affiliated companies

Causal relationship of adverse event

Medical judgment should be used to determine the relationship, considering all relevant factors, including pattern of reaction, temporal relationship, de-challenge or re-challenge, confounding factors such as concomitant medication, concomitant diseases and relevant history. Assessment of causal relationship should be recorded in the case report forms (CRFs). The reason for the decision on causal relationship needs to be provided in the CRF.

Yes: There is a reasonable causal relationship between Trazenta® Tablets

administered and the AE.

Probably Yes: It seems there is a reasonable causal relationship between Trazenta®

Tablets administered and the AE.

Can't be denied: Physician has no clear idea on causal relationship.

No: There is no reasonable causal relationship between Trazenta® Tablets

administered and the AE.

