6.2.3 End of trial and follow-up period

The visit at 156 weeks after starting Trazenta® Tablets treatment or the last visit before discontinuation will be the end of the PMS. There is no follow-up period.

Proprietary confidential information © 2013 Boehringer Ingelheim International GmbH or one or more of its affiliated companies

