7.3.3 Safety analyses

AEs will be coded using lowest level terms of the Medical Dictionary for Drug Regulatory Activities (MedDRA). AEs occurring in routine medical practice will be evaluated. The relationship of an AE to Trazenta[®] Tablets will be assessed by the investigator and the sponsor. An ADR is defined as an AE if either the investigator or the sponsor (or both) assess the causal relationship of Trazenta[®] Tablets either as "Yes", "Probably yes" or "Can't be denied".

The frequency of ADRs will be tabulated by system organ class and preferred term according to the current MedDRA version.

The incidence of ADRs stratified based on patient demographics will also be investigated.

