4. CHANGES IN THE PLANNED ANALYSIS OF THE STUDY

There has been no change in the planned analysis from the statistical methods described in the NIS Protocol.

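### Does the SAP's 7-day on-treatment window for adverse events remove later ADRs and SAEs from the safety tables?

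*SAP*

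**What the plan says.** - SAP 6.1 (Treatment(s)) sets the window: "For safety analyses, data up to 7 days after last treatment intake will be considered as on treatment for AE". A parallel sentence sets 7 days for HbA1c.
- SAP 7.8.1 (Adverse events) specifies the main tables: "The frequency of patients with ADRs and with serious AEs will be summarised by treatment (background medication and total), primary SOC and PT". It states no period. It then defines an ADR by the investigator's or sponsor's causality judgement, again with no period.
- Protocol 7.3.3 (Safety analyses) uses the same test: "An ADR is defined as an AE if either the investigator or the sponsor (or both) assess the causal relationship".
- Protocol 5.2.2.1 (Definitions of adverse events) adds: "Every new occurrence of cancer will be reported as a SAE regardless of the duration between discontinuation of the drug".
- SAP section 4 declares: "There has been no change in the planned analysis from the statistical methods described in the NIS Protocol".
- On the end of observation, Protocol 6.2.3 says that, for a patient who stops early, "the last visit before discontinuation will be the end of the PMS", and that there is no follow-up period. Protocol 6.1 lists an observation "and at the time of discontinuation of administration", and Protocol 3.1 lists one at "156 weeks after the start of treatment, or at discontinuation".

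**The concern.** The sentence in SAP 6.1 opens by addressing the safety analyses, and no other adverse event period appears in the SAP. The windows in Table 6.7: 1 serve efficacy visits, and the onset bands in 7.8.1 only group the time to the first ADR. A programmer could take the 7 days as the counting rule. On that reading, a related event starting on day 20 after the last tablet would not count towards ADR incidence, which SAP 5.1 names as the primary safety endpoint. A cancer found months after stopping would not count towards SAE incidence, the other protocol safety endpoint, although the protocol takes care to collect it. Section 4 would then be wrong to declare no change.

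The sample size argument in Protocol 7.6 makes this look more serious, because it is built on seeing a rare ADR at least once and has almost no spare patients. Protocol 6.2.3 adds to the worry. If observation stopped at the visit before discontinuation, events around discontinuation might not be recorded.

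**Working it through.** **1. What the ADR and SAE texts require**

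| Place | Test for inclusion | Time limit |
|---|---|---|
| Protocol 7.3.3, ADR | causality, by investigator or sponsor | none |
| SAP 7.8.1, ADR | causality, by investigator or sponsor | none |
| SAP 7.8.1, ADR and SAE tables | patients with the event | none |
| SAP 6.1 | classes events to day 7 as on treatment | 7 days, as a label |
| Protocol 5.2.2.1, cancer | must be reported as an SAE | none |

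The two ADR definitions agree, and the table specification adds no condition. A related event on day 20 is an ADR under both documents.

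**2. How the SAP behaves when it does want the restriction**

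SAP 6.3 makes an on-treatment HbA1c value a condition of entry to the efficacy set. The same label is absent from 7.8.1. The time-to-onset table there also has a category for unknown onset, and an event without a usable onset date could not be placed inside a 7-day window. This last point is suggestive only.

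**3. Whether the label has a use without excluding anything**

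SAP 7.8.1 merges repeated occurrences into one episode partly according to whether treatment changed between onsets. Such a rule needs a definition of treatment status at onset. The SAP does not say that the 7-day window supplies it, but the window need not be an exclusion rule to have a purpose.

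**4. The plan's own sample size figure**

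Inputs from Protocol 7.6: N = 3,000, with incidence 0.1% at 95% probability or 0.16% at 99%.

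- Required N at 0.1%: ln(0.05)/ln(0.999) = 2,994.2, so 2,995. The stated 3,000 reproduces.
- Detection at 0.1%: 1 − 0.999^3000 = 95.03%.
- Detection at 0.16%: 1 − 0.9984^3000 = 99.18%.
- Lowest incidence giving 95% with 3,000 patients: 1 − 0.05^(1/3000) = 0.0998%. The tolerated uncounted share of a 0.1% ADR is 1 − 0.099808/0.1 = 0.19%.

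That 0.19% only reflects rounding 2,995 up to 3,000. Any loss from any cause would exceed it, so it says nothing about this window.

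**5. Illustration under the narrow reading**

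Let f be the share of a 0.1% ADR's cases that go uncounted. The documents give no value for f. Detection is 1 − (1 − 0.001(1 − f))^3000.

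| f (assumed) | Detection |
|---|---|
| 0 | 95.0% |
| 5% | 94.2% |
| 10% | 93.3% |
| 25% | 89.5% |

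These figures apply only if the window is the counting rule and if the 0.1% in Protocol 7.6 includes onsets after treatment. Neither is stated.

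**6. The end of observation**

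Protocol 3.1, 6.1 and the last column of the flow chart include an observation at discontinuation. The flow chart note also calls for eCRF entry at discontinuation and whenever an adverse event occurs. Protocol 6.2.3 alone points to the visit before. Taken together, these make loss of events at discontinuation unlikely. The 7-day upper limit does not conflict with 6.2.3, since a limit on classification is compatible with collection that ends sooner.

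**The case for a change.** The best case for a change is that a window introduced for safety analyses ought to govern something, and the SAP never says what. The sponsor guideline and the analysis data set plan may settle it, but neither is available, and 7.8.1 and the SAP reference list give the guideline different titles. Late events are not impossible either. The cancer rule reaches past discontinuation by design, and adverse event data are merged from a second system besides the CRF. A definition that decides the primary safety count arguably belongs in the SAP itself.

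Part of this stands. The link between 6.1 and 7.8.1 is left unsaid, and a sentence on it would do no harm. But it is a gap in detail and not a wrong instruction, because an analyst who applies 7.8.1 as written obtains the protocol's ADR and SAE counts. The charge of an undeclared change depends on the narrow reading, which the text does not establish. The cancer sentence fixes what must be reported and sets no analysis period, so SAP 6.1 does not contradict it.

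Putting unlimited-time tables first and a 7-day version second would be a preference. With no follow-up period, late events are captured patchily, and mixing them with well-captured on-treatment events has its own cost. Either presentation is defensible.

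**Conclusion.** No change to the plan follows. SAP 6.1 labels events and does not remove them. The tables and the ADR definition in SAP 7.8.1 match Protocol 7.3.3, so neither an exclusion of later events nor a departure from the protocol is shown. Few events after day 7 would be collected systematically in any case, since the protocol has no follow-up period.

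No effect on detection probability or sample size can be claimed. The fall from 95.0% to 93.3% at f = 10% rests on an assumed share and on a reading that the text does not favour. The wording of Protocol 6.2.3 is a clerical slip against Protocol 3.1, 6.1 and the flow chart. It can be tidied whenever those passages are next reconciled, and it does not alter the analysis.

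This conclusion assumes that the sponsor guideline and the data set plan do not impose the window as a counting rule. If they did, the tables would be on-treatment tables, and section 4 of the SAP would need to say so.
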